5.2 Exclusion criteria

Potential subjects who meet ANY of the following exclusion criteria are not eligible for enrollment into this study:

1. Previous anti-cancer chemotherapy, immunotherapy or investigational agents < 4 weeks (6 weeks for nitrosoureas or mitomycin C) prior to the first day of study defined treatment. Palliative radiation < 2 weeks, biological therapy within 2 weeks, hormonal therapy within 1 week prior to Day 1 Cycle 1.
2. Prior treatment with a topoisomerase-I inhibitor (e.g., topotecan, irinotecan).
3. Prior malignancy except for non-melanoma skin cancer and carcinoma in situ, unless diagnosed and definitively treated more than 5 years prior to enrollment.
4. Substance abuses, medical, psychological or social conditions that may, in the opinion of the Investigator, interfere with the patient's participation in the study or evaluation of the study results.
5. Known human immunodeficiency virus (HIV) infection due to concerns of potential drug interaction with various antiretroviral agents.
6. Pregnancy or breast-feeding.
7. Concurrent administration or received CYP3A4 inducers or inhibitors within 2 weeks prior to the first day of study drug treatment. Lists including medications and substances known or with the potential to interact with CYP3A4 are provided in **Section 7.3.7**.
8. Patients with chronic or acute GI disorders resulting in diarrhea of any severity grade; patients who are using chronic anti-diarrheal supportive care (more than 3 days/week) to control diarrhea in the 28 days prior to study entry.
9. Major surgery < 4 weeks or minor surgery (e.g. talc pleurodesis, excisional biopsy, etc) < 2 weeks prior to the first day of study defined treatment.
10. Have central nervous system (CNS) metastases (unless the patient has completed successful local therapy for CNS metastases and has been off corticosteroids for at least 4 weeks before starting study therapy). Brain imaging is required in symptomatic patients to rule out brain metastases, but is not required in asymptomatic patients.
11. Uncontrolled intercurrent illness including, but not limited to, ongoing or active infection, symptomatic congestive heart failure, unstable angina pectoris, cardiac arrhythmia, or psychiatric illness/social situations that would limit compliance with study requirements.
12. Unwilling or unable to follow protocol requirements.

5.3 Inclusion of Women and Minorities

This study will be available to all eligible subjects, regardless of race, gender, or ethnic origin. There is no information currently available regarding differential effects of this regimen in subsets defined by race, gender, or ethnicity, and there is no reason to expect such differences to exist. Therefore, although the planned analysis will, as always, look for differences in treatment

effect based on racial and gender groupings, the sample size is not increased in order to provide additional power for subset analyses.

5.4 Subject Withdrawal

It is the right and the duty of the investigator or co-investigator to stop treatment in any case in which emerging effects are of unacceptable risk to the individual subject. In addition, the investigator or co-investigator is to stop treatment of any subject with unmanageable factors that may interfere significantly with the trial procedures and/or the interpretation of results.

A subject must be discontinued from treatment for any of the following reasons:

- The subject or legal representative (such as, a parent or legal guardian) withdraws consent.
- Disease progression.
- The development of unacceptable toxicity for which symptomatic treatment and/or dose reduction are not considered sufficient.
- The development of an intercurrent condition precluding further administration of the treatment.
- The investigator believes it is no longer in the best interest of the subject to receive treatment on the study.
- Pregnancy of the subject.
- Failure to comply with requirements of the study.
- Administrative reasons (e.g., termination of the study by the Principal Investigator).

6 INVESTIGATIONAL PRODUCT

NKTR-102 will be provided by Nektar Therapeutics.

6.1 Active Substance and Source

The investigational drug product (NKTR-102 for Injection) is formulated as a sterile lyophilized powder of NKTR-102 in lactate buffer at pH 3.5, intended for dilution with commercially available 5% dextrose injection (w/w%; D5W) or 0.9% sodium chloride for injection before IV infusion. The pH of the formulation is in the range of 3.2 to 4.2, and NKTR-102 for Injection storage condition is 2°C to 8°C (with a shelf-life of 36 months).

NKTR-102 (drug substance) is light sensitive. The lyophilized drug product (NKTR-102 for Injection) will be supplied in 25 mL Type 1 amber colored glass vials packaged in cartons. Each carton will contain 10 vials of NKTR-102. Each vial contains lyophilized NKTR-102 equivalent to 100 mg of irinotecan. Each vial and carton will be labeled to comply with local regulations.

6.2 Drug Shipment

NKTR-102 will be shipped to participating sites. Each site will document the date of receipt and condition of the shipment. Drug shipment records will be retained by the investigational pharmacist or designee.

6.3 Reconstitution and Handling

The NKTR-102 for injection vial is for single use only. Allow vial(s) to reach room temperature (approximately 30 minutes).

Using pharmacy standard operating procedure, withdraw 20 mL of D5W from a 250 mL D5W infusion bag using sterile needle and syringe and inject into each vial of lyophilized study drug required for a given dose. The final concentration in the vial is now 5 mg/mL. **Note: Normal Saline (0.9% w/w) may also be used as diluent for reconstitution. It is not necessary to remove overfill.**

Gently invert vial for 1-5 minutes until study drug has fully dissolved. Visually inspect vial contents for particulate matter and repeat inspection when study drug is withdrawn from vial into syringe. If any particulate matter is seen, return the syringe contents to the vial and invert several more times.

If the study drug does not fully dissolve and particulates or small matter is identified in the reconstituted NKTR-102, it is recommended that the reconstituted drug in question NOT be used. Please document in the investigational drug accountability log and prepare a new dose for the patient. Please also quarantine the drug in question and contact Nektar with the following additional information:

- i. Details on how the NKTR-102 was reconstituted
- ii. What diluents were used and in what volume(s)?
- iii. How long was the drug product reconstituted for?

Due to the high viscosity, the study drug solution in the syringe may contain trapped bubbles. This is normal.

Inject the required volume of reconstituted study drug back into the 250 mL infusion bag. The final concentration of NKTR-102 in a 250 mL D5W or Normal Saline infusion bag must be within a range of 0.2 to 1.6 mg/mL and 0.16 to 1.6 mg/mL respectively.

Inspect the 250 mL infusion bag for particulates prior to infusion. If the particulates do not clear with gentle inversion, discard the bag, document in the investigational drug accountability log and inform Nektar.

The reconstituted drug may be stored protected from direct ambient lighting at room temperature (15°C to 30°C) for up to 6 hours prior to start of infusion. Other drugs must not be added to the infusion solution.

6.4 Storage and Stability

The Investigator or designate is responsible to store and dispense the investigational product and will ensure that study drug is securely maintained in a locked, limited-access facility, as specified by Nektar Therapeutics and in accordance with the applicable regulatory requirements.

Drug product NKTR-102 for injection and reconstituted infusion solution can be handled in normal room lighting, but should be protected from extensive exposure to light. It is not necessary to cover the IV bag and administration set with sheathing or aluminum foil.

All study drug supplies must be kept in a locked limited access room within the carton they are packaged and refrigerated at 2°C to 8°C, as specified on the drug label.

6.5 Handling and Disposal

The Investigator or designee will be responsible for dispensing and accounting for all investigational drug provided by Nektar Therapeutics exercising accepted medical and pharmaceutical practices. Study drugs must be handled as cytotoxic agents and appropriate precautions taken per the institution's environmentally safe handling procedures. All investigational drugs will be dispensed in accordance with the Investigator's prescription or written order.

All products dispensed will be recorded on a product accountability record. Records of product lot numbers and dates received will be entered on a product accountability form. This record will be reviewed by the Sponsor's staff or representative during periodic monitoring visits. It is the Investigator's responsibility to ensure that an accurate record of investigational drug issued and returned is maintained.

Used vials (excess drug), expired product, and unused vials will be destroyed according to standard practices at the site after properly accounting for the dispensing. Partially used vials of study drug will not be re-used for other subjects.

7 TREATMENT PLAN

7.1 Dosage and Administration

NKTR-102 will be administered 145 mg/m² IV dose over a 90-minute period once every 3 weeks. Cycles will be repeated every 21 days (\pm 3 days). The patient's actual weight at baseline (Day 1 of Cycle 1) will be used. It is not necessary to correct dosing based on ideal body weight. If the patient's weight changes by > 10% during the course of the study, the body surface area and drug doses should be recalculated.

Treatment will be administered in an outpatient basis. Reported adverse events (AEs) and potential risks are described in Investigator's Brochure. Appropriate dose modifications are described in **Section 7.2**. No other investigational or commercial drugs or therapies other than those described below may be administered with the intent to treat the subject.

7.2 Dose Modification Due to Toxicity

All AEs should be assessed according to the NCI-CTCAE version 4.0. In the event of multiple toxicities, dose delays and modifications should occur in accordance with the worst toxicity observed. NKTR-102 dose modifications (reductions or delays) must be recorded for each patient in the appropriate section of the electronic case report form (eCRF).

7.2.1 Retreatment Criteria

To ensure safe use of NKTR-102, subjects must meet requirements with respect to hematopoietic function (Hgb \geq 8.0 g/dL; ANC \geq 1.5×10^9 /L; platelets \geq 75×10^9 /L) prior to initiation of subsequent cycles. Diarrhea must be fully resolved to Grade 0 for at least 7 days without supportive antidiarrheal measures prior to retreatment. Any non-hematologic toxicities must have resolved to baseline or Grade 1 except for alopecia. Supportive care may be implemented in order to ameliorate diarrhea, nausea, vomiting, or myelosuppression. Dose reductions may also be implemented for subjects who experience recurrent or specific severe toxicities.

7.2.2 Treatment Delay

If the patient fails to meet the criteria for re-treatment, treatment may be delayed, followed by an additional evaluation to determine feasibility of retreatment. Initiation of subsequent doses may be delayed for a maximum of 28 days to allow recovery from any toxicity to permit retreatment. Subjects whose treatment delays are \geq 14 days but \leq 28 days due to a drug-related toxicity must initiate their next treatment cycle with a dose reduction. Subjects who require $>$ 28 days delay due to unresolved toxicity must be withdrawn from treatment, unless, in the Investigator's opinion, continuing in the study is of benefit for the patient. In this case, the reason of continuation must be documented.

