
Diarrhea Any Grade
	
Institute supportive care upon first loose stool. (Unless contraindicated, use loperamide). Monitor bowel function; if diarrhea continues with 1st supportive care agent, consider switching to a 2nd agent or add a 2nd agent (unless contraindicated, use diphenoxylate/atropine).
 
Monitor for dehydration, electrolyte abnormalities; correct if present.
 
Administer antibiotic therapy (oral fluoroquinolones) if the patient develops ileus, fevers or Grade 3/4 neutropenia.
 
Subjects should be immediately hospitalized for IV antibiotics therapy if they have evidence of colitis or ileus even in the absence of neutropenia or fever.
 
If worsening diarrhea, octreotide may be attempted.
 
Monitor bowel function for continued need of supportive care.
 
Stop supportive care after the patient is 48 hour without diarrhea.
	
Confirm with the patient that diarrhea is no longer present for ≥ 7 days without having received supportive care prior to retreatment.
 
Treatment may be delayed up to 28 days; after this, contact Medical Monitor.

Grade 1
	
If still present within 7 days prior to treatment hold therapy until diarrhea is no longer present for ≥ 7 days without having received supportive care.
	
Maintain dose level; consider prophylactic anti-diarrheal supportive care

Grade 2
	
If still present within 7 days prior to treatment hold therapy until diarrhea is no longer present for ≥ 7 days without having received supportive care.
	
↓ 1 dose level after 1st occurrence. ↓ 1 dose level after 2nd occurrence. Discontinue patient after 3rd occurrence.

Grade 3/4
	
If still present within 7 days prior to treatment hold therapy until diarrhea is no longer present for ≥ 7 days without having received supportive care.
	
↓ 2 dose level after 1st occurrence. Provided that adequate supportive care has been given to the patient, discontinue patient after 2nd occurrence. If the patient has not received adequate supportive care, retreatment may be attempted for a 2nd episode of Grade 3 diarrhea (re-instruct patient on supportive care). Patients must be discontinued for a 2nd episode of Grade 4 diarrhea.

Dehydration		

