Grade 1 or Grade 2	Consider anti-emetic and/or anti-diarrheal therapy. If Grade 2 present on a treatment day, hold therapy for a week or until toxicity resolves to baseline or Grade \leq 1, with a maximum of 28 days.	Consider prophylactic anti-emetic therapy. Maintain dose level.
Grade 3	Use anti-emetic and/or anti-diarrheal therapy. If present on a treatment day, hold therapy for a week or until toxicity resolves to baseline or Grade \leq 1, with a maximum of 28 days.	Consider prophylactic anti-emetic therapy. \downarrow 1 dose level after 1st occurrence; \downarrow 1 dose level after 2nd occurrence Discontinue patient after 3rd occurrence
Grade 4	Use anti-emetic therapy and IV fluids. Consider hospital admission. If present on a treatment day, hold therapy for a week or until toxicity resolves to baseline or Grade \leq 1, with a maximum of 28 days.	Use prophylactic anti-emetic therapy. \downarrow 2 dose level after 1st occurrence. Discontinue patient after 2nd occurrence.
Nausea / Vomiting / Abdominal Pain		
Grade 1 or Grade 2	Consider anti-emetic therapy. If Grade 2 present on a treatment day, hold therapy for a week or until toxicity resolves to baseline or Grade \leq 1, with a maximum of 28 days.	Consider prophylactic anti-emetic therapy. Maintain dose level.
Grade 3 or Grade 4	Use anti-emetic therapy. Consider administration of IV fluids. If present on a treatment day, hold therapy for a week or until toxicity resolves to baseline or Grade \leq 1, with a maximum of 28 days.	After 1st occurrence use prophylactic anti-emetic therapy and maintain dose level \downarrow 1 dose level after 2nd occurrence Discontinue patient after 3rd occurrence
Other Drug-Related Non-Hematologic Toxicities (Except Fatigue/Asthenia and Alopecia)		
Grade 1 or Grade 2	Consider supportive care as appropriate. If Grade 2 present on a treatment day, hold therapy for a week or until toxicity resolves to baseline or Grade \leq 1, with a maximum of 28 days.	Maintain dose level (for Grade 2 toxicity, the Investigator may use discretion to \downarrow 1 dose level after 1 st occurrence depending on the nature of the toxicity).
Grade 3 or Grade 4	Use supportive care as appropriate. If present on a treatment day, hold therapy for a week or until toxicity resolves to baseline or Grade \leq 1, with a maximum of 28 days.	\downarrow 1 dose level after 1 st occurrence; supportive care as appropriate. \downarrow 1 dose level after 2 nd occurrence. Discontinue patient after 3 rd occurrence.

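### Section 7.2.2 requires a dose reduction after a 14–28 day drug-related delay, five Table 3 rows say to maintain the dose, and neither text is given precedence

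*Combined protocol and SAP*

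**What the plan says.** **Section 7.2.2 (Treatment Delay)** works by length of delay.
- General cap: "Initiation of subsequent doses may be delayed for a maximum of 28 days to allow recovery from any toxicity to permit retreatment".
- Delay of at least 14 and at most 28 days: patients delayed "due to a drug-related toxicity must initiate their next treatment cycle with a dose reduction". Grade does not enter.
- Delay over 28 days: patients "must be withdrawn from treatment, unless, in the Investigator's opinion, continuing in the study is of benefit for the patient", with the reason documented.

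**Table 3 (Section 7.2.3)** works by type of toxicity, grade and occurrence. Its right-hand column gives the next-cycle dose according to the worst toxicity in the prior cycle; length of delay is not a criterion in any row.
- Grade 1 or 2 dehydration, and Grade 1 or 2 nausea/vomiting/abdominal pain: "If Grade 2 present on a treatment day, hold therapy for a week or until toxicity resolves to baseline" or Grade 1, capped at 28 days. The dose cell reads "Consider prophylactic anti-emetic therapy. Maintain dose level".
- Grade 1 diarrhea: hold until the patient has been free of diarrhea, without supportive care, for at least 7 days. The dose cell reads "Maintain dose level; consider prophylactic anti-diarrheal supportive care".
- Diarrhea of any grade: "Treatment may be delayed up to 28 days; after this, contact Medical Monitor".

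Section 7.2.3 ties the 25 mg/m² reductions to the conditions in Table 3, permits two, bars re-escalation, and discontinues a patient who would need a third.

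**The concern.** A patient with a drug-related hold of 14 to 28 days can meet a mandatory reduction in one place and an instruction to maintain the dose in the other. The choice carries forward: a reduction cannot be undone, and it brings the patient one step nearer to discontinuation. Section 4.2 describes a multi-site study, so sites reading the two texts differently would treat like patients differently. Sections 11.5 and 11.6 plan toxicity and adverse event summaries by dose level, and these would then partly reflect which text a site followed. A lesser uncertainty of the same kind concerns whether treatment may continue after 28 days, and on whose decision.

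**Working it through.** The plan states no figure here to reproduce. The check is a row-by-row comparison of Section 7.2.2 with Table 3.

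**1. Rows with a hold instruction.** Hematologic Grade 3 and Grade 4 (2); diarrhea Grade 1, Grade 2 and Grade 3/4 (3); dehydration Grade 1/2, Grade 3 and Grade 4 (3); nausea/vomiting/abdominal pain Grade 1/2 and Grade 3/4 (2); other drug-related non-hematologic Grade 1/2 and Grade 3/4 (2). Total: 2 + 3 + 3 + 2 + 2 = 12. The febrile neutropenia row has no hold text. The any-grade diarrhea row gives general instructions and is taken up in step 5.

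**2. Rows that say maintain.** Five of the 12:

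| Table 3 row | Hold allowed | Table 3 dose | Section 7.2.2 after a 14–28 day drug-related delay |
|---|---|---|---|
| Diarrhea, Grade 1 | Until at least 7 days clear; 28 days from the any-grade row | Maintain | Reduce |
| Dehydration, Grade 1/2 | For Grade 2, up to 28 days | Maintain | Reduce |
| Nausea/vomiting/abdominal pain, Grade 1/2 | For Grade 2, up to 28 days | Maintain | Reduce |
| Nausea/vomiting/abdominal pain, Grade 3/4 | Up to 28 days | Maintain at first occurrence only | Reduce |
| Other drug-related non-hematologic, Grade 1/2 | For Grade 2, up to 28 days | Maintain; Grade 2 reduction at the investigator's discretion | Reduce |

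In the remaining 12 − 5 = 7 rows Table 3 itself reduces or discontinues, so maintain-versus-reduce does not arise.

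**3. Cases.** Drug-related Grade 2 dehydration held for 21 days: Section 7.2.2 says reduce, Table 3 says maintain. Grade 1 diarrhea that continues 7 days past the planned treatment day and then needs 7 clear days gives a delay of 7 + 7 = 14 days, which reaches the Section 7.2.2 threshold while the row says maintain.

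**4. Search for a precedence rule.** Section 7.2 has a worst-toxicity rule, but it covers multiple toxicities, not section against table. Section 7.2.1 says only that reductions may be made for recurrent or specific severe toxicities. Section 7.2.3 points to Table 3 conditions, which do not include length of delay. None ranks the two texts.

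**5. Beyond 28 days.** Section 7.2.2: withdrawal, unless the investigator judges that continuing is of benefit and documents why. Any-grade diarrhea row: contact the Medical Monitor. The 12 − 3 = 9 hold rows outside diarrhea: 28 days as a maximum, with no exception. The three diarrhea grade rows carry no limit of their own.

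**6. Size of one step.** 25 / 145 = 0.172, about 17% of the starting dose. The permitted levels are 145, 145 − 25 = 120, and 120 − 25 = 95 mg/m², so one reduction uses half of what is allowed.

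**The case against.** The best defence is that the two texts have different triggers and can be layered. On that reading, a Table 3 instruction to maintain means only that the grade does not call for a reduction, while Section 7.2.2 adds a mandatory one once a drug-related delay reaches 14 days. The table's management column is headed as recommended guidelines, whereas Section 7.2.2 is mandatory; no single cell says to maintain after 14 days or more; and the permissive wording of Section 7.2.3 does not make Table 3 the only basis for reduction.

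This is a plausible reading, and possibly the intended one, but it is not written down. It fits least well in the row for other Grade 1/2 toxicity, where Table 3 leaves a Grade 2 reduction to discretion and Section 7.2.2 would compel it. It also leaves open whether, where Table 3 already takes one step, a long delay is satisfied by that step or adds another.

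On delays over 28 days the defence is stronger. Section 7.2.2 states the same 28-day cap and then an explicit exception, and a contact step for diarrhea can coexist with an investigator's decision. What remains is that the nine capped rows do not mention the exception and that the decision-maker for prolonged diarrhea is unclear.

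A reader might infer that Table 3 as a whole contradicts Section 7.2.2. It does not: seven of 12 hold rows are free of the maintain-versus-reduce conflict, Section 7.2.2 requires reduction only for drug-related delays, and the Medical Monitor referral is confined to diarrhea.

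**Conclusion.** The inconsistency is real but bounded. It covers five of 12 hold rows, one at first occurrence only, and only when the delay is drug-related and lasts 14 to 28 days. The differing texts on continuation after 28 days are a secondary point. Each affected decision moves the dose by 25 mg/m² (17% of 145 mg/m²) and uses one of two irreversible reductions.

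A reader might go further and infer an effect on the primary result, since Section 11.1 counts patients who come off study and start other therapy before week 18 as failures. The documents do not support that step: they do not report how often such delays occur, and nothing in them links one dose step to progression-free status at 18 weeks. The 85.5% diarrhea incidence in Section 1.5 is not a rate of delays of 14 days or more. Sample sizes and decision rules are unaffected. This is a drafting inconsistency with consequences for dosing and safety reporting, and it should be corrected. The conclusion assumes that Sections 7.2 to 7.2.3, as supplied, contain the full dose-modification instructions.

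**What to change.** Reconcile Section 7.2.2 with Section 7.2.3 and Table 3 so that both give the same instruction on two matters:

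1. The dose after a 14–28 day delay due to drug-related toxicity, explicitly for the five rows listed. If the two texts are meant to operate together, say so, and say whether a reduction already required by Table 3 satisfies Section 7.2.2.
2. Whether treatment may continue after a delay of more than 28 days and who decides, with the diarrhea row and the nine rows that state a 28-day maximum worded to match.

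Which rule should apply is for the clinical team; no view is taken here. The cost is protocol wording, plus the IRB approval that Section 15.1 requires for revisions. No change to sample size, decision rules or data collection is needed, since Section 7.2 already has dose reductions and delays recorded for each patient.
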